3.2 Allocation to Treatment Groups and Blinding

We will prepare a set of sealed files (sealed envelopes or a virtual / digital analog), with appropriate numbers for the eScreen condition and for Usual Care. Each file will contain directions for either: a) proceeding with the eScreen system or b) proceeding with the Usual Care condition.

We will randomize in blocks (2-to-1 ratio of eScreen to Usual Care within each block). Randomization files will be prepared at CHOP and released in blocks at each of the two study sites. As each participant is enrolled, and after completion of baseline measures, research staff will open the next available file and proceed with the designated activity.

Participants, as well as research staff conducting the baseline assessment visit, cannot be blinded as to study condition. Research staff conducting the T2 and T3 follow-up assessments will be blinded to the family's study condition. These staff will not have access to study tracking sheets that indicate condition, and will not participate in meetings in which case allocation is discussed. Questionnaires regarding acceptability of the eScreen system will be administered separately for those families in the eScreen condition.

3.3 Study Duration, Enrollment and Number of Sites

3.3.1 Duration of Study Participation

The study duration per subject will be up to approximately 12 weeks, with (a) one brief screening / baseline assessment, (b) for the eScreen group only: intermittent involvement (using eHealth tools at home) over a 6 week period, and (c) two brief follow-up research assessments at approximately 6 weeks and 12 weeks post-baseline.

3.3.2 Total Number of Study Sites/Total Number of Subjects Projected

The study will be conducted at 2 investigative sites: CHOP and the University of Kentucky.

Recruitment will stop when approximately 300 randomized child-parent pairs are enrolled. It is expected that approximately 300 randomized child-parent pairs will need to be enrolled to produce 127 evaluable families for completer analysis.

3.4 Study Population

We will enroll children (and one parent per child) at CHOP or KCH (N=300 child-parent pairs ; plus up to 10 child-parent pairs in a pilot phase) who meet the following criteria.

3.4.1 Inclusion Criteria

- Child age 8 – 17 years
- Child treated or admitted for injury or illness event that occurred within the past month
- Child has regular access to a compatible (IOS or Android) tablet at home
- Parent has an internet-capable smartphone and can receive text messages on that phone, OR has email account that can receive messages about child status
- Child and parent read or understand English well enough to consent / assent to participation and complete study tasks (e.g., checklists, use of screening system)

3.4.2 Exclusion Criteria

- Index medical event is injury due to family violence.

Subjects that do not meet all of the enrollment criteria may not be enrolled. Any violations of these criteria must be reported in accordance with IRB Policies and Procedures.

4 STUDY PROCEDURES

4.1 Screening & Baseline Research Assessment

Research staff will approach parents to describe the study, review eligibility criteria, and invite their and their child's participation. We will obtain parent consent, followed by child assent, for study participation. We will document consent/assent via RedCap or on paper. Consent / assent will include child and parent agreement that, if assigned to the eScreen group, the child will be asked to sign in and play the eScreen game at least 3 times per week for 6 weeks. (Children may play more often, and beyond the 6 week time frame if they choose.)

At enrollment (T1), before randomization, children and parents will complete baseline research assessments (see Table 2 in Section 5). Following baseline assessments, study staff will open a file to reveal the condition to which the child is assigned. Those randomized to the eScreen group will then receive sign-in instructions for the mobile / online interface, practice signing in, and begin to play the eScreen game. (Parents will be introduced to these procedures so they can assist their child if needed.)

We will make every effort to approach parents and children in person to obtain consent / assent and initiate study procedures. In cases where an eligible participant / parent is missed at the hospital or clinic and during periods when we are unable to conduct in-person enrollment for public health reasons, we may obtain consent / assent (via REDCap or telephone) when staff are not present with the family. (See Section 9.6) After consent / assent are obtained, we will administer baseline (T1) study questionnaires verbally or online for parent and child. Following completion of T1 assessments, study staff will open a file to

reveal the condition to which the child is assigned. Those randomized to the eScreen group will then receive sign-in instructions for the mobile / online interface. We will also offer to schedule a phone call at a convenient time for the family to answer any questions about the sign-in process and encourage children to practice signing in and begin to play the eScreen game. (Parents will be introduced to these procedures so they can assist their child if needed.)

4.2 Study Treatment Phase

Over the next 6 weeks, children in the eScreen group will be expected to play the game at least 3 times per week, and will be able to play the game more often if they want to. Reminders to parents will encourage children to play at least 3 times per week.

Each instance of game play will include an embedded eScreen assessment of current pain, PTSS and functional recovery (unless the child has completed this assessment within the past 24 hours).

For the eScreen group, the system will provide templated weekly messages (weeks 1 to 6) to parents regarding child pain, PTSS, and functional recovery. Design of message timing and delivery mode is based on lessons from stakeholder interviews in Phase I. Message content and specific screening algorithms are derived from our team's prior studies. Parent messages (sent via text or email per parent preference) will include information drawn from evidence-based resources on pain and PTSS, with links to more information as appropriate.

The research team will provide parents at CHOP and UK with a study-specific CHOP email and phone number which they can use to alert the team of any technical difficulties with the system.

4.3 Follow-up

For both study groups, research assessments at T2 (6 weeks post-T1) and T3 (12 weeks post-T1) will repeat baseline measures and also assess pain interference and impairment from PTSS – see Table 2 in Section 5. Additional outcomes will be gathered from parents at T3 and abstracted from medical records and each hospital's Trauma Registry (for injured children).

At the completion of each research assessment, all participants will be provided with a message about talking with their primary care provider if they have any concerns about physical or emotional recovery. Depending on context of measure administration, this will be delivered verbally by study staff and/or as a written message at the end of self-administered questionnaires in the REDCap system. Additionally, when a T2 or T3 research assessment indicates that a child is currently experiencing high pain or may meet symptom criteria for posttraumatic stress disorder, we will inform parents and suggest that they check in with their child and consider contacting their child's doctor.

After completion of their T3 assessment, children in the Usual Care group will be provided with sign-in information and offered the opportunity to play the game. For this group, we

will not administer eScreen in-game assessments. We will ask about the child's perceptions of game use – via a modified TAM questionnaire.

Study teams at CHOP and UK will complete the follow up research assessments for CHOP and UK subjects.

4.4 Subject Completion/Withdrawal

Subjects may withdraw from the study at any time without prejudice to their care. They may also be discontinued from the study at the discretion of the Investigator for lack of adherence to study protocols. The Investigator may also withdraw subjects who violate the study plan, or to protect the subject for reasons of safety, or for administrative reasons. It will be documented whether or not each subject completes the study.

5 STUDY EVALUATIONS AND MEASUREMENTS

5.1 Screening and Monitoring Evaluations and Measurements

5.1.1 Medical Record Review

Variables that will be abstracted from the medical record:

- Age
- Gender
- Race
- Ethnicity
- Medical diagnos(es) for this admission or ED/outpatient visit
- For injured children, date and mechanism / circumstances of injury
- For children with a medical event (other than injury), date of onset and circumstances of current complaint
 - e.g., for children with SCD, date of onset and any circumstances related to onset of pain crisis or other medical event that precipitated their specialty care or ED visit or their admission

5.2 Efficacy Evaluations

5.2.1 Diagnostic Tests, Scales, Measures, etc.

Measures used in analyses of primary and secondary study objectives are in **bold** in Table 2. More detailed information about each of these measures is presented in Section 1.3.2. Other measures are used to assess sample descriptives or covariates, or are used in exploratory analyses. Timing of each assessment is also presented in Table 2.

Table 2. Study measures by reporter, mode of delivery, and time point.

Measure	Construct	Reporter	In-game*	Assessments*		
				T1	T2	T3
Demographic & health form	Demographics and child health / health utilization	Parent**		X		
eScreen pain screener: Analog	Current pain intensity	Child	X			

pain scale						
eScreen PTSS screener: ASC- 6	Current traumatic stress symptoms	Child	X			
eScreen functional recovery screener: "Back to Normal"	Current functional recovery	Child	X			
Numerical Rating Scale (NRSI)	Current pain intensity	Child		X	X	X
Colored Analogue Scale	Current pain intensity	Child		X		
PROMIS Pediatric Pain Interference	Impact of pain on functioning - past wk	Child / Parent**			X	X
Parent Post-op Pain Measure (PPPM)	Current pain intensity	Parent*		X	X	X
PROMIS Sleep Disturbance Short Form	Sleep problems (covariate)	Child / Parent**		X	X	X
Child PTSD Symptom Scale for DSM5 (CPSS-5)	Traumatic stress symptoms & impairment from these symptoms	Child		X	X	X
PTSD Checklist for Children – Parent Report (PCL-C/PR) – adapted for DSM5	Traumatic stress symptoms & impairment from these symptoms	Parent**		X	X	X
Pediatric Quality of Life Inventory (PedsQL-C & -P) Acute Version	Functional recovery / Health-related quality of life - past wk	Child / Parent**		X	X	X
Health and Recovery Questionnaire	Health status & follow-up care ***	Parent**			X	(X)
Parent Information / Confidence Questionnaire	Management of child health & recovery	Parent			X	X
Technology Acceptance Model (TAM) questionnaire (eScreen group only)	Perception of eScreen system utility & acceptability	Child / Parent			X	
Modified Technology Acceptance Model (TAM) questionnaire (Usual Care group only – optional with game play after T3)	Perception of game and acceptability	Child				optional after T3
* Timing of assessments: T1 = at enrollment in hospital / clinic; T2 = 6 wks post-T1; T3 = 12 wks post-T1; plus, for eScreen group only: In-game assessment at T1 and at each subsequent game session						
** Parent reporting on child symptoms / functioning						
*** Health and Recovery Questionnaire admin at T2, but if T2 is missed will admin at T3						

5.3 Safety Evaluation

This is a minimal risk study. There is no known physical risk for subjects of completing measures of pain or stress symptoms, nor in using a prototype screening system.

6 STATISTICAL CONSIDERATIONS

6.1 Primary Endpoint

The primary study endpoints employ validated measures of ongoing symptoms / problematic recovery: pain (NRSI rating), pain interference (PROMIS Pain Interference T score) and PTSS presence and related impairment (CPSS-5 scores) at T2 (6 weeks post-baseline).

Reflecting our primary aim of prediction, the primary study endpoints are not participant scores on these measures, but rather the results of ROC analyses; i.e. the area under the curve (AUC) for eScreen pain score predicting pain and pain interference and the AUC for eScreen PTSS score predicting PTSS symptom presence and related impairment.

6.2 Secondary Endpoints

The secondary study endpoint relates to the potential impact of the eScreen system on parent management of child symptoms and recovery. We will compare eScreen and Usual Care groups on parent ratings at T2 of the extent to which they (a) have received the information they needed to take care of their child after leaving the clinic or hospital, and (b) have felt confident in taking care of their child (related to their illness / injury) in this 6 week period.

6.3 Statistical Methods

We will first conduct descriptive analyses of key variables, examine missing data, and consider whether the distribution of any key study variables warrants alternative, non-parametric analyses. All primary study analyses use child self-report measures; we collect additional parent-report measures of some variables for use in later exploratory analyses.

6.3.1 Baseline Data

Baseline and demographic characteristics will be summarized by standard descriptive summaries (e.g. means and standard deviations for continuous variables such as age and percentages for categorical variables such as gender).

6.3.2 Efficacy Analysis

Primary endpoint

Hypothesis: Results of eScreen-delivered in-game assessments will predict ongoing symptoms / problematic recovery at T2 (6 weeks post-baseline), i.e. in ROC analyses, good to excellent AUC ($\geq .80$) for prediction of problems as follows: eScreen pain score predicting pain (NRSI ≥ 6) and pain interference (PROMIS pain interference T score ≥ 65); eScreen PTSS score (ASC-6) predicting PTSS (significant PTSS indicated by CPSS-5 symptom endorsement) and impairment from PTSS symptoms (impairment endorsed on CPSS-5).

Analyses: In ROC analyses, we will estimate AUC as a global indicator of predictive efficiency of eScreen results in detecting children with clinically meaningful ongoing symptoms or problematic recovery. We will then calculate sensitivity and specificity for dichotomous indicators predicting presence of these problems using cutoff scores based on results of prior studies:

- eScreen pain indicator (pain score ≥ 6) predicting pain and pain interference (NRSI / PROMIS scale);
- eScreen PTSS indicator (ASC-6 ≥ 6) predicting PTSS and related impairment (CPSS-5);
- eScreen functional recovery indicator predicting reduced HRQoL (PedsQL-C score < 70).

After primary analyses with a priori cutoffs, we will use results of ROC analyses to examine potential adjustments to cutoff scores for eScreen-delivered measures to optimize prediction

of problems. Given the system's aim to detect children whose ongoing symptoms or problematic recovery might otherwise be missed (to allow parents and providers to further assess and respond in a timely manner) the goal for eScreen cutoff scores is to optimize sensitivity while maintaining reasonable specificity.

Secondary endpoint

Hypothesis: At T2, compared to the Usual Care group, the eScreen group will demonstrate higher parent information and confidence in managing child symptoms and recovery.

Analyses: All analyses comparing groups will be conducted first on an intent-to-treat basis. We will calculate Cohen's d as the between-group difference in summed parent information / confidence ratings, standardized by the pooled SD for the groups.

Exploratory analyses:

We have already examined concurrent validity in a prior study, but will conduct exploratory analyses in this new sample to determine the association between scores on brief child-report measures delivered via the eScreen system and scores on validated measures administered by trained research staff at the closest available research assessment.

After primary study analyses above, we will examine the ability of the eScreen measures to predict the same outcomes at a more distal point (T3: 12 weeks post-baseline).

We will also examine whether eScreen performance varies by child sex, age, race/ethnicity, or socio-economic status.

In exploratory analyses to better understand eScreen performance, we will examine a) the association of eScreen measures with sleep disturbance, parent-reported medication usage, new medical concerns, and service utilization, b) the potential impact of relevant child history (prior injury or illness, hospital admission, trauma exposure) on eScreen performance, and c) prediction of parent-reported outcomes (pain / pain interference, PTSS / impairment, HRQoL).

Results of these exploratory analyses will inform future development and deployment of the eScreen system.

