The secondary study endpoint relates to the potential impact of the eScreen system on parent management of child symptoms and recovery. We will compare eScreen and Usual Care groups on parent ratings at T2 of the extent to which they (a) have received the information they needed to take care of their child after leaving the clinic or hospital, and (b) have felt confident in taking care of their child (related to their illness / injury) in this 6 week period.

TABLE 1: SCHEDULE OF STUDY PROCEDURES

Study Phase	Screening and Baseline	Intervention (use of eHealth tools at home)	Follow-up (phone, online, or mail)		
Visit Number	T1		T2	T3	post-T3 (optional)
Informed consent / assent	X				
Review inclusion / exclusion criteria	X				
Demographics / medical history	X				
Complete study questionnaires	X		X	X	
Randomization	X				
eScreen group: Use eScreen system (child screening and parent information components)		X			
Usual Care group: Optional use of game & feedback on game					X

FIGURE 1: STUDY DIAGRAM

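### Blocks are released by site, but the stated secondary comparison has no site term or interval, and a single summed score cannot separate the two parts of the secondary objective (minor)

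*Combined protocol and SAP*

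**What the plan says.** **Allocation (Section 3.2).** Allocation is blocked, with two eScreen places to every Usual Care place inside a block. On where the blocks are used, the section says: "Randomization files will be prepared at CHOP and released in blocks at each of the two study sites". The word stratified is not used. Even if one common list is cut into blocks and shared out, each site still works through complete 2:1 blocks, so the arms are balanced within site.

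**Analysis (Section 6.3.2, secondary endpoint).** "All analyses comparing groups will be conducted first on an intent-to-treat basis". The only statistic then given is Cohen's d, "as the between-group difference in summed parent information / confidence ratings, standardized by the pooled SD for the groups". No site term, covariate, test or interval is named. Section 6.3 adds a general option of non-parametric methods. Section 5.2.1 says some measures serve as covariates, and Table 2 labels the sleep scale as one, but no model uses them.

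**Endpoint.** The Abstract and Sections 2.2 and 6.2 give two parts: (a) information ("a) have received the information they needed to take care of their child after leaving the clinic or hospital") and (b) confidence in caring for the child. Table 2 schedules the "Parent Information / Confidence Questionnaire" at T2 and T3 only, so the outcome has no baseline value.

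**Numbers.** Section 3.3.2 expects that "approximately 300 randomized child-parent pairs will need to be enrolled to produce 127 evaluable families for completer analysis". Section 6.4 splits these as 85 eScreen and 42 Usual Care.

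**The concern.** When the randomisation balances a factor that also predicts the outcome, leaving that factor out of the analysis counts its variance as noise, although the design has already removed it from the arm difference. The interval is then a little too wide and the test a little too cautious. The mismatch is largest where within-site balance is best kept, which is the intent-to-treat set that the plan puts first.

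Two reporting gaps go with this. Section 6.4 describes the purpose of the comparison as estimating effect sizes, yet no interval is promised around d. And if only one total is shown, a reader cannot tell whether parents gained information, confidence or both.

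**Working it through.** **1. The plan's own figure.** Section 6.4 says 85 vs 42 detects d = .49 with 80% power at alpha up to .05. The SE of a difference in SD units is sqrt(1/85 + 1/42) = .1886. Two-sided detectable d = (1.960 + .842) × .1886 = .528, and power at .49 is about 74%. One-sided, it is (1.645 + .842) × .1886 = .469. Neither gives .49. That is a separate matter and nothing below depends on it.

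**2. What the assumed site effect means.** The documents give no share of outcome variance due to site, so .02, .05 and .10 are assumed. With two equal sites (also assumed), the gap between site means in within-site SDs is sqrt(R² / [.25 × (1 − R²)]) = .29, .46 and .67.

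**3. Type I error of the unadjusted test, all 300 analysed.** With arms balanced within site, the true variance is (1 − R²) times the variance the test assumes, so the error is 2 × [1 − Φ(1.96 / sqrt(1 − R²))]:
- R² .02: 1.96/.990 = 1.980, giving 4.8%
- R² .05: 1.96/.975 = 2.011, giving 4.4%
- R² .10: 1.96/.949 = 2.066, giving 3.9%

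**4. The same with 127 of 300 analysed.** Loss to follow-up loosens within-site balance. Simulation (60,000 trials per setting, blocks of 6, sites 50:50 or 70:30, loss at random, all assumed; Monte Carlo SE 0.09 points) gave 4.65% to 4.91%. With a site term, error was 4.86% to 5.23% across all settings, including 70% and full retention.

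**5. Interval width with a site term.** Ratio to unadjusted = sqrt[(1 − R²) × (N − 3)/(N − 3 − k)], where k is the number of added terms and the second factor is the cost of chance imbalance. With N = 127 and k = 1, that factor is 124/123 = 1.008:

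| Site R² | Width ratio | Change |
|---|---|---|
| 0 | 1.004 | 0.4% wider |
| .02 | .994 | 0.6% narrower |
| .05 | .979 | 2.1% narrower |
| .10 | .953 | 4.7% narrower |

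**6. Adding four T1 variables as well.** With k = 5 the factor is 124/119 = 1.042. At a total R² of .02, .05 or .10 the interval is 1.1% wider, 0.5% narrower or 3.2% narrower. Break-even is R² = 5/124, about 4%.

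**7. The missing interval.** SE(d) = sqrt[N/(n1 × n2) + d²/(2N)]. For an observed d of .49 at 85 vs 42: sqrt(127/3570 + .2401/254) = .191, a 95% CI of .12 to .86. At 200 vs 100: sqrt(300/20000 + .2401/600) = .124, a CI of .25 to .73.

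**8. What the sum can show.** For two parts with equal SDs and correlation r, summed d = (d1 + d2)/sqrt(2 + 2r). At an assumed r of .5:
- .50 and 0: .50/1.732 = .29
- .25 and .25: .50/1.732 = .29
- .50 and .50: 1.00/1.732 = .58

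At r of .3 or .7 the first two cases again coincide, at .31 or .27.

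**The case against.** The strongest reply is that almost nothing is at stake for validity. The comparison is randomised, the estimate is unbiased, and the test errs on the cautious side. At the planned 127 families the departure from 5% is a few tenths of a point. No site effect is documented, the comparison is secondary, and Section 3.1 says the study is powered for the primary aims. All of this stands, and it is why the point is minor.

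Section 5.2.1 does mention covariates, so reading the analysis as unadjusted rests on silence. That is fair, but the mention is tied to no model and site is not named.

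The parent scale is one instrument, so a sum is a natural lead result. Section 1.3.2 refers to an Appendix for more on the measures, which may hold the scoring. A reader might infer that only a total will be reported; Section 6.3.2 does not say so. What stands is that it does not promise the parts either.

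A reader might also infer that several T1 variables, such as the "Parent Post-op Pain Measure (PPPM"), should be added for a worthwhile gain in precision. The documents do not support this. The outcome has no T1 value, nothing shows that any T1 variable predicts parent information or confidence, and a five-term model loses precision below an R² of about 4%.

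Finally, the projected loss of 173 of 300 families (58%) matters more to this comparison than a site term, which does not address it.

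**Conclusion.** The point holds as a minor, nearly free improvement to the secondary analysis. Allocation is balanced within site and the stated analysis does not use this. The cost of leaving site out is a type I error of about 3.9% to 4.8% at full retention, close to 5% at 127 analysed, and an interval wider by up to about 5% than it need be. These figures rest on an assumed site R² of .02 to .10; the simulated ones also assume block size, site split and loss at random.

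Two parts need no R² at all. An effect size without an interval says little when d = .49 at 85 vs 42 is compatible with .12 to .86. And a single total cannot answer both halves of Section 2.2.

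It would be wrong to conclude that the planned estimate is biased or its test invalid. The primary AUC aim uses the eScreen group only and is unaffected.

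**What to change.** In Section 6.3.2, secondary endpoint:
- Estimate the T2 arm difference in the summed score, intent-to-treat first, with a linear model containing arm and site.
- Report the difference with its 95% CI. Divide it by the unadjusted pooled SD, so that the planned d keeps its meaning, and give d a 95% CI too.
- Keep the summed score as the lead result and say how it is formed. Show (a) information and (b) confidence beside it, each with a 95% CI and no further confirmatory test.

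The cost is a few sentences of text. Site is known for every family and no new data are needed. If site explains nothing, the interval at 127 families widens by about 0.4%. Showing the parts without extra confirmatory tests adds no multiplicity.
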